## 7.0 SCREENING AND RECRUITMENT

Patients will be identified and recruited through Urology outpatient clinics located at the Medical Arts and Research Center (MARC), University Hospital System (UHS), and the South Texas Veterans Healthcare System Audie L. Murphy Hospital in the genitourinary (GU) clinic. Eligible patients will be approached at the time of their standard of care visit. The inclusion of subjects, or refusal to participate in this study, will not affect the health care they will receive.

Once a subject is identified who may meet eligibility criteria, the provider and/or approved research staff will explain to each potential subject the research purpose, voluntary nature of participation, study procedures, risks and benefits of participation, alternatives available and the subjects' rights and responsibilities. The informed consent process will be carried out by personnel who are IRB trained and designated for that role. There is no waiting period required before enrolling. The participant may decline to

participate, decide to participate, or take the consent home to think about participating. Subjects will consent in a private room, and usual privacy policy practices followed. Study procedures and objectives will be described to them, and they will be given a copy of the informed consent document. Subjects will also be given contact information for someone they can call with any questions. No study procedures will occur until the patient has signed the informed consent.

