Remote Consent/Waiver of documentation of informed consent: Eligible subjects undergoing standard of care visits via telephone, video conference or telemedicine will be consented remotely in the absence of face-to-face contact. The purpose of remote consent is to allow the study investigator/designee and potential subject to engage in the informed consent process similar to what would be conducted face-to-face under normal circumstances. Initially, subjects will be introduced to the study by urology provider and explain the consent process. Subjects will be informed that a consent form will be sent via e-mail, mail or fax. Following delivery of the consent form, approved research staff will call subject and conduct the consent interview via telephone when the subject can read the consent form during the discussion. Research staff will confirm subject's name and date of birth from subject before discussion to ensure the identity of the subject. If agreed to participate, subject will provide verbal consent. No study procedures will occur until the subject and research staff have provided verbal consent.

Each participant will be assigned a unique subject identifier (subject ID) that has no meaning external to the study database. The participant identifiers will be further masked and password protected, and stored only on a secure server behind a "firewall." Only the PI of the IRB approved protocol ([name]) and approved research staff will have access to these identifiers. A research study file will be kept for each participant accrued. This file will include the participant's consent, the assigned unique subject identifier, research records, and copies of relevant source documents. All participant records will be securely stored in the Urology research offices. A data entry system will be prepared in RedCap, Excel, or equivalent software interface for the study. Both the subject identifier and sequence number for each patient will be entered into the database together with clinical outcome data collected across visits.

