### **8.1 Enrollment (research)**

After shared decision making with their physician, if patients have elected to undergo a urologic stone procedure that will require transurethral surgery and access to the urinary system, the study team will be alerted. After screening the chart to confirm inclusion and exclusion criteria are met, the approved study team will approach for enrollment and engage in informed consent process.

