## **8.4 Randomization (research)**

A randomization list will be generated using a computer-based-random number generator [www.randomizer.org](http://www.randomizer.org). Randomization will be created 1:1, n=110 per group. Once created, individual envelopes will be created, and study staff will pull an envelope after the participant signs consent. The research staff will not be blinded to the randomization groups. The standard of care group will have urine culture results directed to treating physician. The intervention group will have NGS results sent to Infectious Disease pharmacist, [name] to provide an antibiotic recommendation. The antibiotic recommendation, along with NGS results, will then be provided to treating physician. The physician will then utilize these tools to select the best antibiotic for the case but is not required to abide by the ID pharmacist's recommendation. The standard of care group will have a urine sample sent to MicroGen Dx, but the results will not be provided to the physician.

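### Section 8.4 has unblinded enrolling staff pull envelopes, without specifying list order, an independent list holder or a log, and the study calendar allows randomization to be repeated

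*Combined protocol and SAP*

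**What the plan says.** - **List (Section 8.4).** "A randomization list will be generated using a computer-based-random number generator", and "Randomization will be created 1:1, n=110 per group". No block size, strata or list custodian is given.
- **Draw (Section 8.4).** "Once created, individual envelopes will be created, and study staff will pull an envelope after the participant signs consent".
- **Blinding (Section 8.4).** "The research staff will not be blinded to the randomization groups".
- **Who enrols (Section 8.1).** After chart screening, "the approved study team will approach for enrollment and engage in informed consent process".
- **Who collects the outcome (Section 8.7).** Study staff, by chart review and/or telephone about 7 to 14 days after surgery.
- **Remote patients (Section 7.0).** "If agreed to participate, subject will provide verbal consent". The trigger in Section 8.4 is a signature, which these patients do not give.
- **Repeat procedures (Section 6.0).** The Randomization row carries footnote 2, under which the marked procedures may be done again if the culture is not within 45 days of the operation. No text says that the first assignment stands.
- **Analysis (Section 10.0).** A chi-squared test of the primary outcome, and a logistic regression adjusted for observed covariates that are not named.

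**The concern.** In an open trial, random allocation protects the comparison only if nobody who decides on a patient's entry can know or change the next assignment. Here the people who pull the envelope have already read the chart. They can know whether percutaneous nephrolithotomy (PCNL) is planned, and Section 3.0 says that PCNL carries a higher infection rate than ureteroscopy. If an envelope can be seen beforehand, taken out of turn or replaced, risk can be shifted between arms, and the result would read as an effect of sequencing. A repeat randomization after a second urine sample is another route to a different arm. Both routes are selection rather than chance imbalance, so stratifying the list would not close them.

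**Working it through.** **1. Safeguards set against the text**

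| Safeguard | What the document provides |
|---|---|
| Unpredictable list | Computer-generated, 1:1 |
| Consent before the draw | Yes for signed consent; verbal consent not covered |
| Envelopes sealed, opaque, numbered, used in list order | Not specified |
| List holder separate from enrolling staff | Not specified |
| Entry locked or time-stamped before the arm is seen | Not specified |
| Log of draws reconciled to the list | Not specified; Section 7.0 records a sequence number per patient but does not link it to an envelope |
| One assignment per patient | Not stated; calendar footnote 2 permits a repeat |

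The first safeguard is present and the second is partly present. The others cannot be shown from the text.

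**2. The plan's own figure.** The plan gives no figure for allocation. The nearest is 85 per group (Section 10.0). With unpooled variance, (1.960 + 0.842)² × (0.11×0.89 + 0.01×0.99) / 0.10² = 84.6, so 85 reproduces. It is not at issue here.

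**3. What steering could do (illustration only)**

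Inputs from the document: systemic inflammatory response rates of 7.1% after ureteroscopy and up to 27% after PCNL (Section 2.0), an average infection rate of 11%, and 110 per arm. Assumptions: these rates stand in for infection, there is no true effect, and an imbalance d in PCNL share has been created.

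- Implied PCNL share: s = (0.11 − 0.071)/(0.27 − 0.071) = 0.039/0.199 = 0.196. That is 43 of 220, or 21.6 per arm.
- Arm rates: 0.071 + (s ± d/2) × 0.199, so the false difference is 0.199 × d.
- d = 0.10: 12.0% against 10.0%, a false 2.0 points. It takes 5.5 PCNL patients moved out of the NGS arm (26% of 21.6), exchanged for ureteroscopy patients.
- d = 0.20: 13.0% against 9.0%, a false 4.0 points. It takes 11 patients (51%).

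Exact binomial probability that the two-sided 5% test falsely favours NGS:

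| Per arm | d = 0 | d = 0.10 | d = 0.20 |
|---|---|---|---|
| 110 | 2.6% | 7.1% | 15.8% |
| 150 (about 300 in the synopsis) | 2.5% | 7.9% | 19.5% |

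**4. The same scenario with adjustment.** A Mantel-Haenszel test stratified by PCNL, 110 per arm, 400,000 simulated trials: 2.5% with no gap and 2.4% at both gaps. Adjusting for a recorded factor removes the bias from that factor. It does nothing for selection on something not recorded.

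**5. Guessing from running counts.** Suppose a guesser always names the arm that lags. For a permuted set of m + m, the expected number correct is m + (4^m/C(2m,m) − 1)/2.

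- m = 110 (the list, read as one permutation): 118.8 of 220 = 54%. Over the last 20 assignments, 65% by simulation.
- Blocks of 4: 2.83/4 = 71%. Blocks of 6: 4.10/6 = 68%. Blocks of 8: 5.33/8 = 67%.
- Blocks of 4 and 6 mixed equally: 6.93/10 = 69%.

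The single long list is therefore harder to guess than small blocks. The weakness lies in how the envelopes are handled, not in the list.

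**The case against.** The strongest reply is that this is silence, not a stated fault. A list implies an order, and competent staff may well use sealed, numbered envelopes without the protocol saying so. The envelope comes after consent, so a patient is already in the study when the arm is seen. Section 10.0 also plans an adjusted model, and procedure, stent status and medical history are all recordable. Footnote 2 appears on eight calendar rows with the same pair of marks, so its place on the Randomization row may be a blanket annotation.

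Much of this stands, and it rules out several stronger readings:

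- A reader might infer that the envelopes are unordered, or that enrolling staff hold the list. The document says neither; it leaves both open.
- A reader might infer from the three recruitment locations that one stack serves all of them, or from telephone consent that nobody else sees a remote draw. The document does not describe where envelopes are kept or who is present.
- A reader might take 7.1% or 15.8% as the plan's error rate. Those figures need an assumed amount of steering, proxy risks (one of them an upper figure) and no adjustment for procedure. The amounts assumed are not small: 26% and 51% of the PCNL patients who would have been in the NGS arm.

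What the reply does not answer: consent before the draw helps only if the next assignment cannot be seen or exchanged, and nothing ensures that. The adjusted model covers observed covariates only. Whatever was intended by the footnote, as printed it allows a second randomization.

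**Conclusion.** The point holds as a gap in the allocation method. As written, Section 8.4 does not protect against foreknowledge or re-drawing of an assignment, and the Section 6.0 footnote leaves repeat randomization open. The same unblinded study team screens, consents and collects the outcome, and analysis afterwards cannot restore concealment for unrecorded factors.

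The document does not show that concealment has been lost or that anyone would steer patients. No size of bias can be derived from it. The figures above show only that, under their stated assumptions, moderate steering would matter in an unadjusted test and that steering on procedure alone would be removed by adjusting for procedure. The case for change rests on the missing safeguards and the low cost of adding them.

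**What to change.** Amend Section 8.4 as follows.

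1. The list is generated and held by a named role that does not enrol patients.
2. The arm is released only after identity, consent (signed or verbal), eligibility and planned procedure are saved and locked with a time stamp. The REDCap randomisation module can do this if REDCap is the platform chosen. Section 7.0 leaves that open: "A data entry system will be prepared in RedCap, Excel, or equivalent software interface for the study".
3. Otherwise, use sealed, opaque, consecutively numbered envelopes, opened in order after the patient's ID and the date are written on them. Keep a log and reconcile it to the list at the six-monthly source verification already planned in Section 11.0.
4. State that the first assignment stands if urine collection is repeated, and remove footnote 2 from the Randomization row in Section 6.0.
5. Do not add small permuted blocks. In this open trial they would raise the share of correct guesses from 54% to about 67–71%.

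The cost is a short amendment and minor set-up work. The REDCap route also needs a computer at the point of allocation. No extra patients or study procedures are required.

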## 1.0 STUDY SYNOPSIS

This is a randomized controlled clinical study evaluating the use of next-generation sequencing (NGS) to improve antibiotic prescribing before ureteroscopy or percutaneous nephrolithotomy. NGS will be performed on voided urine collected as routine care approximately 30 days prior to surgery. Results will be presented to ID pharmacist within 48-72 hours to help select the most appropriate antibiotics, and independently as part of routine care, surgeons will choose the antibiotic that they would use in each case, while the ID pharmacists would select their optimum choice. Pharmacists will account for site-specific antibiotic stewardship practices, allergies, medication adjustments, and C. difficile rates. Approximately 300 subjects will be randomly assigned in a 1:1 ratio to receive either NGS antibiotic recommendation or standard of care (SOC) prophylaxis prescribed treatment. All providers within the Department of Urology who perform urologic stone procedures (n=5) will also be approached in person with an information sheet. Subjects assigned to standard of care will have urine cultures sent for analysis, and the physician will choose antibiotics based on results as per usual practice. Subjects assigned to the NGS group, in addition to routine urine culture results, will have NGS urine culture results sent to an ID pharmacist, and recommendations will be shared with the physician to determine the antibiotic selection. The physician will ultimately decide the appropriate antibiotics to prescribe. Approximately 7-14 days after surgery, the research staff will conduct a telephone call to ask about any post-operative infections, complications, and any additional antibiotics that were prescribed.

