## **8.7 Follow-up phone call contact (research)**

The study staff will conduct a chart review and/or telephone follow up approximately 7-14 days post urologic procedure to assess for complications, infections related to the procedure, and antibiotics prescribed. In the event an infection or complication related to the procedure is identified by study staff before patient's clinical follow up visit, study staff will alert medical team and provider if patient has not done so.

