#### **8.8 Clinic follow up (standard of care)**

The chart will be reviewed for infections missed on phone calls.

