### **10.0 METHOD OF ANALYSIS/STATISTICS**

**Next Generation Sequencing:** Standard of care whole urine will be collected (approximately 30-50 mL) utilizing special vacutainers supplied by MicroGen Dx. Approximately 5-10mL of urine taken for culture will be sent to MicroGen Dx, a CAP-accredited and CLIA licensed clinical diagnostic lab, for analysis. MicroGen Dx will perform rapid PCR for common resistance genes prior to ureteroscopy or percutaneous nephrolithotomy. The plan will be to run target bacterial or fungi DNA on the quantitative PCR (qPCR) panel assay on the Roche LightCycler 480 II instrument and sequencing of 16S ribosomal RNA hypervariable regions V1-V2 using Ion Torrent (Ion Torrent PGM).

**Microbiome:** Sequencing reads were demultiplexed using QIIME2 software and denoised using dada2 software, using a phred score threshold of 28. Alpha diversity will be measured using the Shannon index, and a Wilcoxon test was used to determine whether the Shannon index differed between patients with stents and those without stents at the time of urine collection. Principle coordinates analysis (PCoA) of Bray-Curtis dissimilarity will be performed to visualize differences in species composition between patients with and without stents, and Linear discriminant analysis Effect Size (LEfSe) analysis was conducted to identify differentially abundant taxa between stent and non-stent groups.

**Sample size:** This will be a randomized trial of Microgen Dx versus standard of care. The primary endpoint is infection within 14 days of surgery. The primary objective of the study is to evaluate whether Microgen Dx reduces an infection rate compared to the standard of care. The null hypothesis is that infection rates within 14 days of surgery are the same between the randomization arms. The alternative hypothesis is that infection

rates within 14 days of surgery are not equal between the randomization arms. The infection rates are assumed to be 11% in the control arm and 1% in the experimental arm based on our preliminary data. A sample size of 85 per group will give 80% power to detect a 10% difference in infection rate when the two-sided Z-test with alpha=0.05 is used. Demographics and potential confounding factors will be summarized by randomization arm. A logistic regression model will be used to measure the association between the primary outcome and treatment arm with adjustment for the observed covariates.

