**Statistical analysis:** Our primary outcome is infection after surgery as a dichotomous outcome. We will utilize a chi-squared analysis to determine the difference between intervention and control groups. We will assess demographics between groups using chi-squared for dichotomous variables and Student's t-test for continuous variables. Additionally, we will investigate the utilization of antibiotic in a mixed-model regarding a number of antibiotics and antibiotic class utilization.

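### The primary endpoint, infection, has no case criteria and is ascertained by staff who know the arm, with no masked classification, so differential labelling could bias the comparison

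*Combined protocol and SAP*

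**What the plan says.** **Definition.** Section 10.0 words the endpoint twice. Under Sample size: "The primary endpoint is infection within 14 days of surgery". Under Statistical analysis: "Our primary outcome is infection after surgery as a dichotomous outcome". Neither statement carries diagnostic criteria, and none appear elsewhere. SIRS and sepsis are mentioned only in the background (Section 2.0).

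**Ascertainment.** Section 8.7: "The study staff will conduct a chart review and/or telephone follow up approximately 7-14 days post urologic procedure", the purpose being "to assess for complications, infections related to the procedure, and antibiotics prescribed". Section 4.0 has the same arrangement. The synopsis (Section 1.0) mentions only the call: "the research staff will conduct a telephone call to ask about any post-operative infections, complications, and any additional antibiotics that were prescribed". No script for the call and no rule for judging relatedness to the procedure is given.

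**Blinding.** Section 8.4: "The research staff will not be blinded to the randomization groups". Under Section 4.0 (Case Study Creation) and Section 8.4, the treating physician receives the NGS report and the pharmacist's recommendation in the intervention arm and neither in the control arm. Receiving them reveals the arm.

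**Checks.** Section 8.8: "The chart will be reviewed for infections missed on phone calls". Section 8.3 collects laboratory, vital-sign and diagnosis data. Section 11.0 provides six-monthly source verification and an annual audit. None of these is said to be masked, and none supplies infection criteria.

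**The concern.** A binary endpoint without criteria leaves room for judgement. A patient's telephone account of fever or burning, an empirical antibiotic course, or a positive culture without symptoms could each be counted or not. The wording in Section 8.7 adds a second undefined judgement, whether an infection was related to the procedure. Because method of follow-up may be chart, telephone or both, the evidence can also differ from patient to patient.

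When those making or feeding these judgements know the arm, errors need not balance between arms. Random allocation does not protect against this, and labels assigned with knowledge of the arm cannot be reliably corrected in the analysis. At stake is whether a significant difference reflects fewer infections or different counting. A larger sample does not help: a fixed difference in labelling becomes more likely to reach significance as the sample grows.

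Timing is also open. Contact may take place at day 7 while the endpoint runs to day 14, and no rule says how the remaining days are covered.

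**Working it through.** **Inputs from the plan.** Infection 11% in control and 1% in the experimental arm, two-sided alpha 0.05, 85 per group (Section 10.0); 110 per group (Section 8.4); 250 completers, or 125 per arm at 1:1 (Section 8.0); about 300 randomised, or 150 per arm (Section 1.0). The totals differ, so each was run.

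**The plan's own figure.** With unpooled variance, n = (1.96 + 0.84)² × (0.11×0.89 + 0.01×0.99) / 0.10² = 84.6, rounded up to 85. The stated sample size reproduces.

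**Input that is assumed.** The plan gives no misclassification rates. Let m be the share of NGS-arm infections that go unrecorded, with none missed in control. The true rate is 11% in both arms, so there is no effect.

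**Method.** Let x_C and x_N be the recorded events, n the number per arm, and p̄ = (x_C + x_N)/(2n). The uncorrected chi-squared test is equivalent to

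Z = [(x_C − x_N)/n] / √[p̄(1 − p̄)·2/n].

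The rejection probability is the sum of Bin(x_C; n, 0.11) × Bin(x_N; n, 0.11(1 − m)) over all outcomes with |Z| > 1.96, computed exactly.

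| m | recorded NGS rate | n = 85 | n = 110 | n = 125 | n = 150 |
|---|---|---|---|---|---|
| 0 | 11.0% | 5.0% | 5.3% | 5.0% | 5.0% |
| 10% | 9.9% | 5.6% | 6.1% | 5.9% | 6.1% |
| 20% | 8.8% | 7.6% | 8.8% | 8.9% | 9.7% |
| 30% | 7.7% | 11.2% | 13.8% | 14.5% | 16.3% |
| 50% | 5.5% | 25.0% | 32.7% | 35.2% | 40.7% |

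Under this assumption most of the rejections favour NGS. At 110 per arm and m = 30%, 13.6 of the 13.8 points do. If the under-recording were in control instead, the same figures would apply with the direction reversed.

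**How many labels matter.** This depends on where the result starts.

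- From equal arms at 11%, significance needs 7 of 9 NGS-arm infections unrecorded at 85 per arm (9 v 2, Z = 2.18), 8 of 12 at 110 (12 v 4, Z = 2.08) and 10 of 16 at 150 (16 v 6, Z = 2.21).
- Near the threshold, one label is enough: at 110 per arm, 12 v 5 gives Z = 1.77 and 12 v 4 gives Z = 2.08.
- Near the planned effect, at 85 per arm, adding two NGS-arm cases to 9 v 1 gives 9 v 3 (Z = 1.80) and significance is lost. At 110 per arm, 12 v 1 remains significant after three are added (12 v 4).

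**The case against.** The strongest reply has four parts.

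- **Existing checks.** The chart review in Section 8.8 works directly against under-recording. Section 8.3 collects laboratory and diagnosis data, and Section 11.0 provides source verification and audit. These make one-sided omission of 30% or 50% less plausible, and that stands. But they are not stated to be masked, they have no criteria to check against, and a search for missed infections does not verify positives that rest on a call alone.
- **Assumed error.** No document supports any particular value of m, or its direction. This also stands. At 10% the false-positive rate barely moves, to about 6%.
- **Inferred facts.** A reader might infer that the same individuals open envelopes, telephone patients and decide who was infected. The text says study staff in some places and research staff in others, and names nobody who makes the final call. A reader might also infer competing endpoint definitions from the mentions of SIRS and sepsis. Those are background only; the aim and the endpoint consistently say infection. The gap is absent criteria.
- **Limits of masking.** Masked classification of flagged cases cannot recover infections that were never flagged. This is correct, so the remedy must also make case-finding independent of arm.

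Unblinded care is probably unavoidable in this design. Unblinded classification is not.

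**Conclusion.** The point holds as a risk created by the plan as written: a primary endpoint without criteria, ascertained by unblinded staff, partly from records written by physicians who know the arm, with no masked classification. It is a worthwhile improvement rather than a demonstrated bias.

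Its size rests wholly on assumed, one-directional error. With no true effect and 11% in both arms, the false-positive rate ranges from little above nominal when 10% of NGS-arm infections are missed to 25-41% when half are. The documents do not say where in that range the trial would fall.

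Two stronger readings are not supported. One is that relabelling two or three borderline cases would decide the trial. That is true only of results near the threshold; from equal arms it takes 7 of 9 or 8 of 12. The other is that labelling would favour NGS. The stated hypothesis makes that plausible, but nothing in the documents establishes it.

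**What to change.** Before any outcomes are seen:

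1. Prespecify one set of objective infection criteria that can be verified from records and that covers every patient through day 14. The choice of criteria belongs to the investigators.
2. Use the same scripted call and the same search of chart, laboratory and prescription records for every patient in both arms, so that case-finding does not depend on arm.
3. Have each potential case classified from a summary with arm, NGS and pharmacist information removed, by an existing team member who neither randomised nor treated that patient.
4. State that this classification is the one used in the primary analysis.

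The cost is a criteria form, a call script and a small amount of extra review. Treatment, randomisation and enrolment do not change. The recorded event rate may move away from the assumed 11% in either direction, depending on the criteria, so power should be rechecked against them. Clinicians who know the arm will still decide which tests to order, so the risk is reduced but not removed.
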